5.1. Analysis Datasets

Primary Analysis Set

The primary analysis set to evaluate whether DCE-MRI can detect differences in measures of pulmonary oedema or vascular permeability between HV and HF patients will include all subjects in the evaluable population. A sensitivity analysis for V_e will also be performed using the safety population.

This analysis set will also be used to explore the effect of exercise on DCE-MRI measures in HV and HF patients. Missing post-exercise MRI data will not be imputed. This analysis set will be used to estimate the intra-subject variability of DCE-MRI measures of pulmonary oedema and vascular permeability.

Secondary Analysis Set

The secondary analysis set will include all evaluable subjects who have MRI data of sufficient quality from Session 1, 2 or both. This analysis set will be used to estimate the intra-subject variability of DCE-MRI measures of pulmonary oedema and vascular permeability.

No formal hypothesis testing will be performed.

No analysis will be performed for Group 3, so no analysis data sets will be defined.

6. TREATMENT AND OTHER SUB-GROUP DESCRIPTIONS FOR DATA DISPLAYS

Population Group		Final Data Display (i.e. HARP / other)
Code	Treatment Description	Treatment Description
HV	Healthy Volunteer	Healthy Volunteer
HF	Heart Failure Patient	Heart Failure Patient
ADHF	Acute Decompensated Heart Failure	Acute Decompensated Heart Failure Patient

7. GENERAL CONSIDERATIONS FOR DATA ANALYSES AND HANDLING

7.1. Reporting Conventions

Data manipulations and statistical analyses will be performed using SAS version 9.2 or higher.

All variables will be presented and summarized in tables or graphs. Continuous variables will be summarized using descriptive statistics (mean, standard deviation, median, interquartile range (where appropriate), and range). Categorical variables will be summarized using frequency counts and percentages. Associated listings will also be provided. Unless otherwise stated, 95% confidence intervals around the point estimates, as appropriate will be presented.

7.2. Data Management

Data Type	Source	Format of Data	Planned Date of Final File ¹	Responsibility
Safety	Database	IDSL	DBF	CPSSO
PD/biomarker	Study Site	CSV file	DBF	CPSSO

1. This is for study teams to determine upfront if there is a possibility of not meeting the completion of the CPSR within 6 months of LSLV (i.e. novel data that may not be available until several months after LSLV).

7.3. Premature Withdrawal and Missing Data

All subjects who withdraw prematurely from the study will be documented and the reason for their withdrawal recorded in the final Clinical Pharmacology Study Report (CPSR). All available data from subjects who withdraw will be listed and all available planned data will be included in the summaries according to the populations and analysis datasets defined in Section 5.

7.3.1. Missing MRI measurements

Session 1 and Session 2 MRI measurements can be considered baseline pre-exercise data. If Session 2 data is unavailable, Session 1 data will be used. For the purpose of the secondary analysis to estimate intra-subject variability, MRI data will not be imputed.

7.3.2. Missing dyspnoea score and respiratory rate

The last available dyspnoea score or respiratory rate will be carried forward in the case of missing Session 2, and pre-exercise Session 3 measurements. Post-exercise measurements will not be imputed.

Other missing data will not be imputed.

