7.4. Baseline Definition

The Session 2 visit will be considered as the baseline visit for MRI measurement endpoints. If Session 2 data is unavailable, Session 1 data will be used. In terms of change from baseline calculation for statistical analysis, tables below defined the baseline for each endpoint of interests:

Parameter	Baseline Collected			Baseline To Be Used in Analysis / Summaries
	Screening	Session 2/1	Session 3	
MRI scan		X	X	Scan 2

Note: For the parameters of MRI scan, if measurements are missing for Scan 2, then Scan 1 measurements will be used as baseline.

Parameter	Baseline Collected			Baseline To Be Used in Analysis / Summaries
	Screening	Session 2/1	Session 3	
Laboratory biomarker	X		Pre-Excercise	Session 3 Pre-Excercise
Respiratory rate		Post-MRI	Pre-Excercise	Session 3 Pre-Excercise
Dyspnoea Scale Scoring		Post-MRI	Pre-Excercise	Session 3 Pre-Excercise
Gas Diffusion, DL_{co} , DL_{no}		Post-MRI	Pre-Excercise	Session 3 Pre-Excercise
Pulmonary function		Post-MRI	Pre-Excercise	Session 3 Pre-Excercise

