7.5.1. Change from Baseline

The change from baseline will be calculated by subtracting the baseline values from the individual post-exercise values. If either the baseline or post-exercise value is missing, the change from baseline is set to missing as well.

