10.3.3. Comparison of effect of exercise at Scan 3 by group (HV, HF)

The analysis will be based on the Evaluable population. The change from baseline parameters of interest on pre-exercise test to post-exercise test in Scan 3 will be fitted separately using a mixed effect model with subject as a random effect, patient population (HF or HV) as fixed effects. Point estimates and associated 95% confidence intervals (CI) will be constructed to provide a plausible range of values for the mean change from baseline measurements in HV and HF patients in Session 3, and the mean difference between the HV and HF groups. Gas diffusion DLco/DLno and lung function parameters in constant exercise session at Scan 3. Change from baseline pre-exercise workload test to post-exercise test is defined as:

DLco/DLno : Scan 3 post MRI – Scan 3 pre-exercise

Lung function: Scan 3 post MRI – Scan 3 pre-exercise

In addition, NT-ProBNP (heart failure patients only), Dyspnoea Score, Respiratory Rate, parameters for gas diffusion and DLco/DLno will be summarized by planned time and group (HV, HF) at Scan 3 by separate exercise session. The corresponding mean (SE) plots will be provided also.

(keep if already programmed)

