10.3.4. Comparison of exercise test parameters at Scan 3 by group (HV, HF)

The similar analysis as for the primary endpoint (Section 10.3.6) will be presented for exercise test on parameters of interests including Ve/Vco2 ratio at Scan 3 in maximal test and constant exercise session separately. See below for the example sas codes for the analysis:

```
proc mixed data=VEVCo2;
  class subjid atrtgrp ptm;
  model AVAL = ptm atrtgrp ptm*atrtgrp/e3 ddfm=kr outp=pred_one;
  repeated PTM/ subject=subjid type=un;
  LSMEANS PTM*atrtgrp /CL ALPHA=0.05;
  estimate 'HF - HV at CONSTANT WORKLOAD' atrtgrp 1 -1
            PTM*atrtgrp 1 0 -1 0/cl alpha = 0.05;
  estimate 'HF - HV at MAXIMAL EXERCISE' atrtgrp 1 -1
            PTM*atrtgrp 0 1 0 -1/cl alpha = 0.05;
  estimate 'MAXIMAL EXERCISE - CONSTANT WORKLOAD in HF' PTM -1 1
            PTM*atrtgrp -1 1 0 0/cl alpha = 0.05;
  estimate 'MAXIMAL EXERCISE - CONSTANT WORKLOAD in HV' PTM -1 1
            PTM*atrtgrp 0 0 -1 1/cl alpha = 0.05;
  ods output lsmeans = lsm;
```

```

ods output covparms = cov_one;
ods output estimates = est;
run;

```

10.3.5. Relationship between change from baseline MRI scan primary endpoint (Ve, Ktrans) and change from baseline of NT-ProBNP, DLco/DLno and Ve/VCo2

Change from baseline NT-ProBNP at Scan 3 is defined as:

post constant workload exercise test –pre constant workload exercise test

The change from baseline DLco/DLno, Ve/VCo2 is defined as:

Scan 3 post MRI – Scan 3 pre-exercise

The following plots will be presented, for each component of interest as defined above:

A scatter plot, with change from baseline (Ve, Ktrans) on the horizontal axes and change from baseline NT-ProBNP, or DLco/DLno, VE/VCO2 on the vertical axes, using different colours for each population if data permit, i.e. HV and HF will be presented, as appropriate to the data.

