12.5.3.3. Comparison of Dyspnoea Score at baseline by group (HV, HF)Tables

No.	Population	IDSL No. / Example Shell	Title	Additional Programming Notes	Responsibility	Deliverable Priority
11.8	Evaluable	DM1	Summary of Dyspnoea score by visit and session	Use dyspnoea variables at each planned time point, including immediately before and after both exercise tests.	Programmer	SAC

Figures

11.6	Evaluable	Example F	Frequency bar plot of Dyspnoea score by visit		Programmer	SAC
------	-----------	-----------	---	--	------------	-----

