12.5.3.4. Comparison of Respiratory Rate at baseline by group (HV, HF)

Tables

No.	Population	IDSL No. / Example Shell	Title	Additional Programming Notes	Responsibility	Deliverable Priority
11.9	Evaluable	DM1	Summary of Respiratory rate by visit	Use respiratory rate at each planned time point.	Programmer	SAC

Figures

11.7	Evaluable	Example B	Mean (SE) Plot for respiratory rate by visit.	Separate line for HF and HV patients across 3 scans.	Programmer	SAC
------	-----------	-----------	---	--	------------	-----

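### Minor: SAP 7.3.2 does not limit which values may be carried forward, so a missing pre-constant-workload dyspnoea score or respiratory rate literally takes the post-maximal-exercise value

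*SAP*

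**What the plan says.** SAP 7.3.2 gives the rule for the two measures: "The last available dyspnoea score or respiratory rate will be carried forward in the case of missing Session 2, and pre-exercise Session 3 measurements". It adds that post-exercise values are not imputed and that no other missing data are imputed. Neither addition says which values may serve as the source.

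SAP 7.4 introduces its tables with "In terms of change from baseline calculation for statistical analysis, tables below defined the baseline for each endpoint of interests". For both measures it lists Session 2/1 post-MRI and Session 3 pre-exercise as the baseline data collected, and takes the Session 3 pre-exercise value as baseline. It does not say whether that means before the maximal test or before the constant-workload test.

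SAP 7.5.1 states: "If either the baseline or post-exercise value is missing, the change from baseline is set to missing as well". It does not say whether a carried-forward baseline counts as missing.

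The outputs that use the values are:
- SAP 9.2.2 and 9.2.3: descriptive statistics and change from pre-exercise in Session 3.
- Table 11.8 (dyspnoea), with the note "Use dyspnoea variables at each planned time point, including immediately before and after both exercise tests".
- Table 11.9 (respiratory rate), with the note "Use respiratory rate at each planned time point".
- SAP 10.3.3, where both measures "will be summarized by planned time and group (HV, HF) at Scan 3 by separate exercise session". That section closes with the remark "keep if already programmed", so this summary may not be produced.

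**The concern.** A carry-forward rule for a pre-exercise value should draw on a resting value. Protocol 6.10 runs the maximal test to volitional fatigue, limited by dyspnoea or fatigue, and protocol 6.6 takes the respiratory rate immediately afterwards. These two measures are therefore the ones most likely to be raised at that moment. The constant-workload test is at a separate visit, not necessarily on the next day. A program that follows 7.3.2 to the letter would put an exertional reading from one visit into the pre-exercise slot of another. At stake is the descriptive picture of the constant-workload test: the resting level would look too high and, in some cases, the exercise response too small.

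**Working it through.** **Order of readings.** Inputs are protocol 6.1.1 (table and footnotes 6 and 7), 6.5 and 6.6, and SAP 9.2.2 and 9.2.3. For each measure:

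1. Session 1, post-MRI
2. Session 2, post-MRI
3. Session 3 Visit 1, before the maximal test
4. Session 3 Visit 1, after the maximal test
5. Session 3 Visit 2, before the constant-workload test
6. Session 3 Visit 2, after the constant-workload test and before scanning
7. Session 3 Visit 2, post-MRI

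Footnote 6 of the time-and-events table omits reading 6. That reading comes after the slot in question, so the source is the same either way.

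**Applying 7.3.2 literally.** The source is the latest earlier non-missing value.

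| Missing value | Source as written | Source if post-exercise values are barred |
|---|---|---|
| Session 2 | Session 1 post-MRI | Session 1 post-MRI |
| Pre-maximal | Session 2 post-MRI | Session 2 post-MRI |
| Pre-constant-workload | Post-maximal | Pre-maximal |

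Only the third row goes wrong. If the post-maximal value is missing too, the literal rule already falls back to the pre-maximal value.

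**Which outputs can change.** Take a subject with reading 4 recorded and reading 5 missing.

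- Reading 6 or 7 recorded: the pre-exercise entry is affected. The change from pre-exercise is affected too, unless 7.5.1 is applied to collected values only.
- No Visit 2 reading, for example because the subject did not return: the pre-exercise entry can still be filled. The post-exercise value is not imputed, so 7.5.1 sets the change to missing.

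**Size.** The documents give no missingness rate and no expected values. Let e be the post-maximal value minus the unrecorded Visit 2 pre-exercise value, k the number of affected subjects and n the group size.

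- Shift in group mean of the pre-exercise entry = + e × k / n
- Shift in group mean change, where a change exists = − e × k / n

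Protocol 4.1 plans 12 per group, with at least 6 per group completing the third scan. With e = 1 and k = 1: 1/12 = 0.083 and 1/6 = 0.167.

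The next table uses assumed values of e, with k = 1:

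| Measure | Assumed e | Shift at n = 12 | Shift at n = 6 |
|---|---|---|---|
| Dyspnoea (points) | 1 to 3 | 0.08 to 0.25 | 0.17 to 0.50 |
| Respiratory rate (breaths/min) | 5 to 20 | 0.42 to 1.67 | 0.83 to 3.33 |

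The SAP's 0 to 5 dyspnoea coding gives a ceiling of 5/12 = 0.42 or 5/6 = 0.83 points. That requires one subject to span the whole scale, so it says little.

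Both denominators are approximate. The 6 counts evaluable post-exercise MRI, not dyspnoea scores. Tables 11.8 and 11.9 use the Evaluable population, which SAP 5 now restricts by age.

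**The case against.** The best defence reads 7.3.2 together with 7.4. For these two measures 7.4 lists only resting sources, and the values that 7.3.2 fills sit in the same columns. On that reading the chain is Session 1, Session 2, then the first Session 3 pre-exercise value. A missing pre-constant-workload value would be other missing data and stay missing, and the problem would not arise.

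This is possible, but it is not the better reading. SAP 7.4 uses the same Session 3 pre-exercise label for DLco and DLno. Protocol 6.1.1 and 6.11 schedule those in Session 3 only at Visit 2, before the constant-workload test and after the scan, so for them the label must mean pre-constant-workload. SAP 10.3.5 likewise defines the NT-proBNP change as "post constant workload exercise test –pre constant workload exercise test", and Table 11.8 reports readings around both tests. Section 7.3.2 does not refer to 7.4, and 7.4 defines baselines, not sources for imputation. What stands is that 7.4 hints at resting sources, so the post-maximal source looks like an unintended effect of the wording.

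It also stands that the outputs are slight. Section 12 lists no change table for these measures (Table 10.6 covers vital signs), and the notes to Tables 11.8 and 11.9 do not say whether imputed values enter.

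A reader might infer more: that the SAP chose an exertional baseline, that the exercise comparison of ve and ktrans is biased, or that every affected subject has a biased change score. The documents support none of these. The first runs against the hint in 7.4. The MRI analyses do not use these two measures. The third fails whenever no Visit 2 post-exercise value exists. The exploratory endpoints do name both measures for correlation with MRI, but SAP 10.3.5 and Figures 11.301 to 11.306 plan plots only for NT-proBNP, DLco/DLno and VE/VCO2.

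**Conclusion.** The point holds as a minor one. Followed literally, a stated rule gives an unsuitable source for one of the three kinds of value it fills. The effect is confined to descriptive outputs: Tables 11.8 and 11.9, the 10.3.3 summary if kept, any display drawn from the same values, and the Session 3 change in 9.2.2 and 9.2.3 under the further condition shown above. No planned model, model-based confidence interval, ve or ktrans result or scatter plot is touched. The number of affected subjects may be zero, and no expected size can be given.

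The conclusion rests on three assumptions: the SAP's Session 3 pre-exercise wording covers the pre-constant-workload reading; imputed values enter the summaries; and post-maximal values exceed resting ones. For dyspnoea the last also assumes that a higher score is worse, which cannot be checked because the scale is withheld from the public protocol. The correction is worth making before programming because it costs almost nothing.

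**What to change.** Add one sentence to SAP 7.3.2:

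> Only resting values (Session 1 or 2 post-MRI, or an earlier Session 3 pre-exercise value) may be carried forward, most recent first; values taken after an exercise test are never carried forward; if no such value exists, the value stays missing.

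This needs no new data and leaves the first-choice sources for missing Session 2 and pre-maximal values as they are.

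The downside is that the carried value may be older, and that the Session 1 and 2 sources are post-MRI readings. Protocol Table 1 lists worsening dyspnoea when supine as a risk in heart failure subjects, so those readings are not a perfect stand-in for a pre-exercise value. Leaving a missing pre-constant-workload value missing would also close the gap, at the cost of a smaller n.

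Two optional clarifications would help but add no weight to this point: SAP 7.4 could say which Session 3 pre-exercise value is the baseline for each test, and 7.5.1 could say whether a carried-forward baseline counts as present.

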7.4. Baseline Definition

The Session 2 visit will be considered as the baseline visit for MRI measurement endpoints. If Session 2 data is unavailable, Session 1 data will be used. In terms of change from baseline calculation for statistical analysis, tables below defined the baseline for each endpoint of interests:

Parameter	Baseline Collected			Baseline To Be Used in Analysis / Summaries
	Screening	Session 2/1	Session 3	
MRI scan		X	X	Scan 2

Note: For the parameters of MRI scan, if measurements are missing for Scan 2, then Scan 1 measurements will be used as baseline.

Parameter	Baseline Collected			Baseline To Be Used in Analysis / Summaries
	Screening	Session 2/1	Session 3	
Laboratory biomarker	X		Pre-Excercise	Session 3 Pre-Excercise
Respiratory rate		Post-MRI	Pre-Excercise	Session 3 Pre-Excercise
Dyspnoea Scale Scoring		Post-MRI	Pre-Excercise	Session 3 Pre-Excercise
Gas Diffusion, DL_{co} , DL_{no}		Post-MRI	Pre-Excercise	Session 3 Pre-Excercise
Pulmonary function		Post-MRI	Pre-Excercise	Session 3 Pre-Excercise

7.5. Derived and Transformed Data

MRI measures: Median values of k^{trans} , v_e and v_p from multiple images/regions will be calculated for total lung, each lung (left and right) and different lung segments. For each MRI measure parameter there are 7 measurement regions: total lung, left lung, right lung, apical left segment, apical right segment, basal left segment and basal right segment for each MRI measure parameter.

Laboratory Data: The majority of laboratory results will be recorded under a numeric field. Some results may be recorded under a character field where a numeric component

(x) has been preceded by ‘>’ or ‘<’ indicating the true value of x is greater than or less than that given.

To ensure this data is not excluded from any summaries or analysis, any laboratory results recorded as ‘>x’ will be moved to the numeric field with a value of x, similarly results recorded as ‘<x’ will be moved to the numeric field with a value of x. All listings will present the data as recorded.

Age (years): Age will be calculated using the date of the screening visit relative to year of birth, according to the Integrated Data Standard Library (IDSL). In this calculation, date of birth will be imputed based on the assumption that all subjects were born on the 30th June (30 Jun YYYY).

Body Mass Index (BMI) (kg/m²): equals (weight (kg)) / ((height (m))²)

Study Day: Study day will be defined in reference to the DCE-MRI scan date in the corresponding Session. Session 1 – Day 1 will be the DCE-MRI scan date in Session 1, and Session 2 – Day 1 will be the DCE-MRI scan date in Session 2, etc.

7.5.1. Change from Baseline

The change from baseline will be calculated by subtracting the baseline values from the individual post-exercise values. If either the baseline or post-exercise value is missing, the change from baseline is set to missing as well.

7.6. Values of Potential Clinical Importance

7.6.1. Values of Potential Clinical Importance for Healthy Volunteers

Hematology Analyte	Effect	Relative – Low (Multipliers of LLN)	Relative – High (Multipliers of ULN)
White Blood Cell Count		0.67	1.82
Neutrophil Count		0.83	
Hemoglobin	Male		1.03
	Female		1.13
Hematocrit	Male		1.02
	Female		1.17
Platelet Count		0.67	1.57
Lymphocytes		0.81	

Chemistry Analyte	Effect	Relative – Low (Multipliers of LLN)	Relative – High (Multipliers of ULN)
Albumin (mmol/L)		0.86	
Calcium (mmol/L)		0.91	1.06
Glucose (mmol/L)		0.71	1.41
Magnesium (mmol/L)		0.63	1.03
Phosphorus (mmol/L)		0.80	1.14
Potassium (mmol/L)		0.86	1.10
Sodium (mmol/L)		0.96	1.03
Total CO ₂ (mmol/L)		0.86	1.14

Liver Function Test (Healthy Volunteers)

Liver Function Test Analyte	Effect	Potential Clinical Importance (PCI) Range	Unit
ALT/SGPT	High	≥ 2x ULN	U/L
AST/SGOT	High	≥ 2x ULN	U/L
AlkPhos	High	≥ 2x ULN	U/L
T. Bilirubin	High	≥ 1.5x ULN	µmol/L
T. Bilirubin + ALT	High	≥ 1.5x ULN T.Bilirubin + ≥ 2x ULN ALT	µmol/L U/L

ECG Values of Potential Clinical Importance (Healthy Volunteers)

ECG Parameter	Potential Clinical Importance Range (PCI)	Unit
Absolute QTc Interval	>450	msec
Increase from Baseline QTc	>60	msec
PR Interval	<110 and >220	msec
QRS Interval	<75 and >110	msec

ECG Parameter	Potential Clinical Importance Range (PCI)	Unit
Absolute QTc Interval	>450 to \leq 480	msec
Absolute QTc Interval	>480 to \leq 500	msec
Absolute QTc Interval	>500	msec
Increase from Baseline QTc	>30 to \leq 60	msec
Increase from Baseline QTc	>60	msec

Vital Sign Values of Potential Clinical Importance (Healthy Volunteers)

VS Parameter	Potential Clinical Importance Range (PCI)	Unit
Systolic Blood Pressure	<85 and >160	mmHg
Diastolic Blood Pressure	<45 and >100	mmHg
Heart Rate	<40 and >110	bpm

Vital Sign Values of Potential Clinical Importance (Healthy Volunteers)

VS Parameter	Potential Clinical Importance Range (PCI)	Unit
Systolic Blood Pressure (Change from Baseline)	Increase \geq 20 and \geq 40	mmHg
	Decrease \geq 20 and \geq 40	
Diastolic Blood Pressure (Change from Baseline)	Increase \geq 10 and \geq 20	mmHg
	Decrease \geq 10 and \geq 20	
Heart Rate (Change from Baseline)	Increase \geq 15 and \geq 30	bpm
	Decrease \geq 15 and \geq 30	

7.6.2. Laboratory Values of Potential Clinical Importance for Heart Failure Patients

Note $GI/L = 10^9/L = 10^3/\mu L$

Hematology			
Laboratory Test	Units	Change from Baseline of Potential Clinical Concern	Potential Clinical Concern Value
Basophils	GI/L	None	None
Calcitonin	pg/mL	None	>100 pg/mL
Eosinophils	GI/L	None	None
Hematocrit	1	>0.1 decrease	>0.05 below LLN >0.04 above ULN
Hemoglobin	g/L	>25 g/L decrease	>20 g/L below LLN >10 g/L above ULN
Lymphocytes	GI/L	None	<0.5 x LLN
Monocytes	GI/L	None	None
Neutrophils	GI/L	None	<1 GI/L
Platelet Count	GI/L	None	<80 GI/L >500 GI/L
Red Blood Cell Count	TI/L	None	None
White Blood Cell Count	GI/L	None	>1 GI/L below LLN >5 GI/L above ULN

Chemistry			
Laboratory Test	Units	Change from Baseline of Potential Clinical Concern	Potential Clinical Concern Value
Albumin	g/L	None	None
Alkaline Phosphatase	U/L	None	>3 x ULN
ALT	U/L	None	>3 x ULN
AST	U/L	None	>3 x ULN
Bicarbonate (Carbon Dioxide)	mmol/L	None	<16 mmol/L > 40 mmol/L

Chemistry			
Laboratory Test	Units	Change from Baseline of Potential Clinical Concern	Potential Clinical Concern Value
Content)			
Blood Urea Nitrogen	mmol/L	None	>2 x ULN
Calcium	mmol/L	None	<1.8 mmol/L >3.0 mmol/L
Chloride	mmol/L	None	None
Creatinine	umol/L	≥50% increase from baseline	>159 umol/L
Direct Bilirubin	umol/L	None	>1.35 x ULN
Gamma Glutamyl Transferase	U/L	None	>3 x ULN
Glucose (fasting)	mmol/L	None	<3 mmol/L >22 mmol/L
Magnesium	meq/L	None	≤1 meq/L
Potassium	mmol/L	None	>0.5 mmol/L below LLN >1.0 mmol/L above ULN
Sodium	mmol/L	None	>5 mmol/L above LN or below LN
Total Bilirubin	umol/L	None	>1.5 x ULN
Total Protein	g/L	None	>15 g/L above or below LN
Uric acid	umol/L	None	>654 umol/L

Liver Function Test	
Laboratory Test	Potential Clinical Concern Value
ALT	$\geq 2 \times \text{ULN}$ $\geq 3 \times \text{ULN}$ $\geq 5 \times \text{ULN}$ $\geq 8 \times \text{ULN}$ $\geq 10 \times \text{ULN}$ $\geq 3 \times \text{ULN}$ and Total Bilirubin $\geq 2 \times \text{ULN}$
AST	$\geq 2 \times \text{ULN}$ $\geq 3 \times \text{ULN}$ $\geq 5 \times \text{ULN}$ $\geq 8 \times \text{ULN}$ $\geq 10 \times \text{ULN}$ $\geq 3 \times \text{ULN}$ and Total Bilirubin $\geq 2 \times \text{ULN}$
Total Bilirubin	$\geq 1.5 \times \text{ULN}$ $\geq 2 \times \text{ULN}$ $\geq 3 \times \text{ULN}$ $\geq 5 \times \text{ULN}$ $\geq 8 \times \text{ULN}$ $\geq 10 \times \text{ULN}$

Vital Signs

Parameter	Units	Change from Baseline of Potential Clinical Concern	Potential Clinical Concern Value
Systolic BP	mmHg	Decrease $>30 \text{ mmHg}$ Increase $>30 \text{ mmHg}$	$<100 \text{ mmHg}$ $>170 \text{ mmHg}$
Diastolic BP	mmHg	Decrease $>20 \text{ mmHg}$ Increase $>20 \text{ mmHg}$	$<50 \text{ mmHg}$ $>110 \text{ mmHg}$
Heart rate	bpm	Decrease $>30 \text{ bpm}$ Increase $>30 \text{ bpm}$	$<50 \text{ bpm}$ $>120 \text{ bpm}$

ECG

Parameter	Units	Change from Baseline of Potential Clinical Concern	Potential Clinical Concern Value
Heart Rate	bpm	Decrease >30 bpm Increase >30 bpm	Supine: < 50 or > 120 bpm
QRS interval	msec	Increase of > 25% when baseline QRS >100 msec Increase of > 50% when baseline QRS ≤100 msec	>200 msec
QTcB	msec	Increase of > 10% when baseline QTc >440 msec Increase of > 20% when baseline QTc ≤440 msec	>500 msec
QTcF	msec	Increase of > 10% when baseline QTc >440 msec Increase of > 20% when baseline QTc ≤440 msec	>500 msec
PR Interval	msec	Increase of > 25% when baseline PR >200 msec Increase of > 50% when baseline PR ≤200 msec	>300 msec

